7) All fertile males and females must be using effective contraception during treatment and during 14 days after treatment end.

Exclusion criteria

The subject must be excluded from participating in the trial if the subject:

- 1) Is taking or plans to take any prohibited medications as per DAA Product Information or herbal supplements, including but not limited to St. John’s Wort (*Hypericum perforatum*) within 2 weeks of Baseline.
- 2) Is currently using or intends to use barbiturates.
- 3) Is a female and is pregnant or breast-feeding, or expecting to conceive or donate eggs from Baseline and continue throughout treatment, and after the last dose of study medication (as per the regimen requirements), or longer if dictated by local regulations.
- 4) Has any condition or pre-study laboratory abnormality, ECG abnormality or history of any illness, which, in the opinion of the investigator, might confound the results of the study or pose additional risk in administering the study drugs to the subject.
- 5) Had a life-threatening SAE during the screening period.
- 6) Has exclusionary laboratory values as listed below:

Laboratory Assessment	Value
Haemoglobin	< 9.5 g/dL for both males and females
Platelets	< 75 x 10 ³ /μL
Serum albumin	< 3.0 g/dL

	
9) Has Child Pugh-B or C decompensated cirrhosis.
 
10) Has previous HCV treatment-experience.
 
11) Has ongoing severe psychiatric disease as judged by the treating physician.
 
12) Has frequent injecting drug use that is judged by the treating physician to compromise treatment safety.
 
14) Is unable or unwilling to provide informed consent or abide by the requirements of the study.
 
15) Is Hepatitis B surface antigen (HBsAg) positive.

Study design	
The study will be conducted as a phase IV, open-label single arm multicentre trial.
 
A total of 150 participants with chronic hepatitis C virus infection genotype 1 or 4 with recent injecting drug use or receiving OST will be enrolled.
 
The study consists of a treatment phase of 12 weeks and a follow up phase of up to 3 years. Participants will be followed up every 3 months for the first year and every 6 months in year's 2-3 to evaluate treatment response and reinfection.

Treatment of participants	
Participants with chronic hepatitis C infection genotype 1 or 4 will receive 12 weeks of open-label elbasvir/grazoprevir (50mg/100mg) in a once daily fixed combination.

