
Week 8 (+/- 7 days)

- LFTs – ALT only
- Pregnancy test (females of child bearing potential only)
- Serious Adverse Events
- Research specimen collection (EDTA plasma)
- Study questionnaire (Adherence)

End of Treatment (ETR) - Week 12 (+/-14 days)

- Qualitative HCV RNA (where available, otherwise quantitative), (Local laboratory)
- LFTs, FBC and biochemistry
- Pregnancy test (females of child bearing potential only)
- Serious Adverse Events
- Concomitant medication
- Study questionnaires (Abbreviated Behavioural, Adherence, and EQ-5D)
- Research specimen collection (EDTA plasma)

Post Treatment Follow-up Visits

Post Treatment Week 12 (SVR12) - Week 24 (+/- 14 days)

- Qualitative HCV RNA (Where available, otherwise quantitative) (Local laboratory)
- LFTs, FBC and biochemistry
- Pregnancy test (females of child bearing potential only) (at 14 days post end of treatment – home test allowed)
- Serious Adverse Events (up to week 16 (SVR4) only)
- Study questionnaires (Abbreviated Behavioural and EQ-5D)
- Research specimen collection (EDTA plasma)
- Finger-stick point-of-care HCV RNA testing (Sub-study sites only)

Post Treatment Weeks 36 (FU1), 48 (FU2), 60 (FU3), 84 (FU4), 108 (FU5), 132 (FU6) and 156 (FU7) (+/- 14 days)

- Qualitative HCV RNA (Where available, otherwise quantitative) (Local laboratory)
- Study questionnaires (Abbreviated Behavioural)
- Research specimen collection (EDTA plasma)
- Finger-stick point-of-care HCV RNA testing (Sub-study sites only)

If a patient has suspected viral relapse or HCV reinfection HCV RNA sequencing will be performed. No additional sample is required.

Monitoring of HBV reactivation

At screening, all patients will be tested for evidence of current (Hepatitis B surface antigen positive) and prior (anti-Hepatitis B core antibody positive) HBV infection before initiation of treatment. Patients with current HBV infection will be excluded. Patients with evidence of prior HBV infection only will be enrolled.

Patients with evidence of prior HBV infection will be monitored for HBV reactivation and hepatitis flare during HCV treatment and post-treatment follow-up. LFTs will be performed 4-weekly during treatment. In the setting of a clinically significant ALT elevation or symptoms and signs of acute hepatitis, HBV DNA testing will be performed to assess for reactivation. Appropriate management for HBV infection will be initiated by the site investigator as clinically indicated.

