9.3 Future use of biological samples

After the samples have been analysed for the study endpoints as specified in the protocol, remaining samples will be stored for use in future Human Research Ethics Committee approved hepatitis C related research. Additional consent will not be sought for this storage and future use. It is not optional. Subjects not wishing to have their samples stored or used in future hepatitis C related research will not be eligible to participate in this study.

10. Statistics

The statistical team and investigators at the Kirby Institute will be responsible for analysing the study data.

Primary Objective: To evaluate the proportion of patients with undetectable HCV RNA at 12 weeks post end of treatment (SVR12) following elbasvir/grazoprevir therapy among PWID with recent injecting drug use or receiving OST and chronic HCV genotype 1 or 4 infection and evaluate demographic and clinical predictors of non-response.

Hypothesis: *Elbasvir/grazoprevir therapy will lead to SVR12 >90% among PWID with recent injecting drug use or receiving OST and chronic HCV genotype 1 or 4 infection.*

Outcome: The primary endpoint for this aim is the proportion of participants with a treatment response (measured by SVR, undetectable HCV RNA 12 weeks after the completion of therapy).

Statistical analysis: The proportion of people with a response to HCV therapy will be evaluated. Factors associated with treatment response (as measured by SVR) will be assessed by univariate and multivariate logistic regression analyses. Factors hypothesized to be associated with HCV treatment response will be assessed including: sociodemographic factors (housing and education), injecting behaviours (recent injecting drug use prior to and during therapy and type of drug injected), and clinical factors (opioid substitution treatment, HCV genotype, fibrosis stage).

Sample Size: Assuming an overall SVR of 90% (135 of 150), the 95% confidence interval around this estimate will be 84.0% to 94.3%. This study will have robust power to examine the effect of treatment setting on SVR: e.g. 80% power to detect an odds ratio of 0.39 or 2.59 or more extreme (with alpha=0.05) for a variable that is 50% prevalent.

Secondary Objective: Estimate incidence and predictors of HCV reinfection after successful elbasvir/grazoprevir.

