Hypothesis 2.1: The incidence of HCV reinfection following successful elbasvir/grazoprevir therapy will be <8 per 100 p-yrs among people with recent injecting drug use or receiving OST.

Hypothesis 2.2: HCV reinfection will be associated with ongoing \geq daily injecting drug use, and needle and syringe borrowing. OST and high-coverage access to needle and syringes will be associated with reduced HCV reinfection.

Outcome: Incidence of HCV reinfection following successful elbasvir/grazoprevir therapy.

Statistical analysis: Rates of HCV reinfection will be calculated using person-time of observation. The estimated date of reinfection will be calculated as the midpoint between the dates of the last undetectable HCV RNA test and the first detectable HCV RNA test at the time of HCV reinfection. Time at risk will commence at the date of undetectable HCV RNA at end of treatment and end at the first of estimated date of re-infection, death, loss-to-follow up or end of study. Confidence intervals for rates will be calculated using a Poisson distribution.

Cox proportional hazards analyses (or other appropriate regression models) will be used to estimate crude and adjusted hazard ratios and corresponding 95%CI to evaluate factors associated with reinfection. Factors hypothesised to be associated with reinfection include demographic factors (age, sex), injecting behaviours (current injecting drug use, daily injecting, type of drug injected, injecting equipment borrowing), use of needle and syringe programs, and opioid substitution treatment with time-updated co-variables.

Sample Size: Overall, based on previous reports of HCV reinfection among current PWID³², and assuming loss to follow-up is 20% per year, it is estimated that the overall reinfection rate will be 8/100 p-yrs (95%CI 5.3, 11.4; 337 p-yrs of follow-up; 27 reinfections). Overall (135 with successful therapy, 27 reinfections), we will have 80% power to detect a hazards ratio (HR) of 2.94 or greater (with alpha=0.05) for a variable 50% prevalent (e.g. ongoing injecting drug use).

Collateral research

Evaluation of HCV phylogenetics

All participants enrolled in this study with available plasma samples at screening or baseline (HCV RNA detectable) will be sequenced for HCV RNA for evaluation of HCV phylogenetics.

Evaluation of HCV re-infection

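### Does the primary SVR12 analysis need a new rule because Section 10 does not say how participants without an SVR12 result are counted?

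*Combined protocol and SAP*

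**What the plan says.** The primary Outcome paragraph in Section 10 defines the endpoint as "the proportion of participants with a treatment response (measured by SVR, undetectable HCV RNA 12 weeks after the completion of therapy". The Statistical analysis paragraph adds "The proportion of people with a response to HCV therapy will be evaluated" and then describes logistic regression for factors associated with response. The Hypothesis paragraph reads "Elbasvir/grazoprevir therapy will lead to SVR12 >90% among PWID with recent injecting drug use or receiving OST", with no test or decision rule beside it.

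The Sample Size paragraph of the same section states: "Assuming an overall SVR of 90% (135 of 150), the 95% confidence interval around this estimate will be 84.0% to 94.3" per cent. The Synopsis (Study design) says "150 participants with chronic hepatitis C virus infection genotype 1 or 4 with recent injecting drug use or receiving OST will be enrolled". Section 5 gives the same 150 as the number expected to be treated.

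For the secondary objective, Section 10 is fuller. It defines time at risk and the events that end it, says "Confidence intervals for rates will be calculated using a Poisson distribution", and sizes the analysis "assuming loss to follow-up is 20% per year".

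Section 6.1 schedules the endpoint visit as "Post Treatment Week 12 (SVR12) - Week 24 (+/- 14 days". Section 19 defines end of treatment as the date of the last dose.

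**The concern.** The secondary endpoint has rules for censoring and for its interval; the primary endpoint has neither. No section names an analysis set for this trial. None says how a missing or out-of-window SVR12 result, an early stop, a death or a loss to follow-up enters the proportion.

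In an open-label, single-arm trial, the choice between all participants and only those tested could then be made with the results in view. The plan expects appreciable loss in this population, so the two proportions may differ by several points and may fall on opposite sides of 90%. At stake would be the headline estimate itself.

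**Working it through.** **1. The plan's own figure.** Inputs from Section 10, Sample Size: 135 responders of 150, two-sided 95% interval.

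| Method | 95% interval for 135/150 |
|---|---|
| Exact (Clopper-Pearson) | 84.04% to 94.29% |
| Wilson | 84.16% to 93.85% |
| Agresti-Coull | 84.06% to 93.95% |
| Jeffreys | 84.44% to 94.04% |
| Wald | 85.20% to 94.80% |

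Only the exact method gives the printed 84.0% to 94.3%.

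**2. How many might be untested.** The plan's 20% loss per year is stated for reinfection follow-up. Applying it before SVR12 is an assumption.

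- Loss over the 12 post-treatment weeks: 150 × (1 − 0.8^(12/52)) = 7.5, or 5.0%.
- Loss over all 24 weeks: 150 × (1 − 0.8^(24/52)) = 14.7, or 9.8%.
- At 10% per year the two figures are 3.6 and 7.1; at 5% per year, 1.8 and 3.5.

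**3. Responders held at 135, 8 untested (assumed).**

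- All participants: 135/150 = 90.0%, exact interval 84.0% to 94.3%.
- Tested only: 135/(150 − 8) = 135/142 = 95.1%, exact interval 90.1% to 98.0%.

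This is close to a worst case. It draws all 8 untested from the 15 planned non-responders. Eight is also the smallest number at which the exact lower limit passes 90%; with 7 it is 89.3%. At 8 the Agresti-Coull lower limit is 89.99%. If 90% of tested participants truly respond, 135 or more of 142 has a probability of about 2%.

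**4. Testing unrelated to response, 15 untested (assumed).** With about 95% responding among the 135 tested, 0.95 × 135 ≈ 128.

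- Tested only: 128/135 = 94.8% (exact 89.6% to 97.9%).
- All participants: 128/150 = 85.3% (exact 78.6% to 90.6%).
- Difference: 9.5 percentage points.

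**5. How often the two point estimates straddle 90%.** Let m untested ~ Bin(150, q) and r responders ~ Bin(150 − m, p). The table gives P(r/(150 − m) > 0.9 and r/150 ≤ 0.9).

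| Untested, q | p = 90% | p = 92% | p = 95% | p = 97% |
|---|---|---|---|---|
| 2% | 28% | 32% | 9% | 1% |
| 5.0% | 48% | 68% | 50% | 20% |
| 9.8% | 51% | 80% | 95% | 85% |

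Here p is the response rate among the tested. The 92% in the Background is for a cited trial's full analysis set, whose handling of missing results the documents do not give. Using it for p may count missing results twice.

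**6. What the text implies.** The Outcome paragraph takes participants as the base and undetectable HCV RNA as the criterion. Read literally, someone without a result is in the denominator and not in the numerator. The planning base of 150 equals both the number enrolled and the number treated, so those two words do not conflict. The plan does not say that all 15 planned non-responders were tested, so 135 of 150 is compatible with counting missing results as non-response.

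**7. What a stricter rule would cost.** Two repairs suggest themselves, and neither is harmless.

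- Fixing the window at study week 24 ± 14 days conflicts with SVR12 counted from the last dose. A participant who stops at week 8 and is undetectable at week 8 + 12 = 20 meets the protocol's definition but would fall outside the window.
- Calling the hypothesis demonstrated only if the exact lower limit exceeds 90% requires 143 of 150 (95.3%; lower limit 90.6%), since 142 gives 89.8%. With none untested, the chance of reaching 143 is 1.4% at a true 90%, 8% at 92% and 52% at 95%. That would add a decision rule the trial was not sized for.

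**The case for a change.** The strongest case for a change is that a planning figure does not settle how missing data are handled. The 135 of 150 is an assumed result, and the analysis paragraph does not adopt its denominator or its interval. On the plan's own loss rate, extended to the period before SVR12, 5.0% to 9.8% would be untested, and step 5 shows that the two point estimates would then often straddle 90%. A sentence of text would remove the ambiguity at no cost in data.

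Much of this stands. No section states a rule for missing SVR12 results, the choice can move the estimate by several points, and the Sample Size text only implies the answer.

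Three things limit its force. First, the primary objective is estimation: no test, success criterion or stopping decision is tied to 90%, so straddling that value changes a description and not a trial decision. Second, the two figures differ only through the number untested. A report giving the numbers treated, tested and responding lets any reader compute both. Third, the size of the effect rests on assumed numbers. At 2% untested the chance of straddling is 9% at a 95% response and 1% at 97%.

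**Conclusion.** The silence on missing SVR12 results is a genuine gap in detail, but no stated rule or figure is wrong. The endpoint wording, the 135 of 150, the matching counts of enrolled and treated participants, and an interval that only the exact method reproduces all lead to the same analysis: all treated participants as the denominator, no result counted as no demonstrated response, and an exact 95% interval. A competent analyst would do this and show the tested-only figure alongside.

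The possible size is not trivial: 9.5 points in the example with 15 untested, and 5.1 points (95.1% − 90.0%) in the near-worst case with 8. Both rest on assumed numbers untested, and the second also on all 8 being non-responders. Since the 90% hypothesis carries no decision rule, and the obvious stricter wordings would conflict with the endpoint definition or impose a criterion with a 1.4% chance of success at the plan's own 90%, no change to the plan is called for.

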Interferon-free and ribavirin-free DAA HCV therapy with elbasvir/grazoprevir will lead to SVR12 >90% among PWID with recent injecting drug use or receiving OST and chronic HCV genotype 1 or 4 infection.

Secondary Hypothesis

The incidence of HCV reinfection following successful interferon-free and ribavirin-free DAA therapy with elbasvir/grazoprevir will be <8 per 100 p-yrs among people with recent injecting drug use or receiving OST.

Primary Objective

To evaluate the proportion of patients with undetectable HCV RNA at 12 weeks post end of treatment (SVR12) following interferon-free and ribavirin-free DAA therapy with elbasvir/grazoprevir among PWID with recent injecting drug use or receiving OST and chronic HCV genotype 1 or 4 infection and evaluate demographic and clinical predictors of non-response.

Secondary Objective

To evaluate the rate of HCV reinfection up to three years following interferon-free and ribavirin-free DAA therapy with elbasvir/grazoprevir.

Exploratory Objectives

- 1) To evaluate factors associated with SVR12 (e.g. drug use at baseline and during therapy, adherence);
- 2) To evaluate the adherence to therapy and associated factors;
- 3) To evaluate safety and tolerability;
- 4) To evaluate injecting risk behaviours during and following HCV treatment;
- 5) To evaluate HCV phylogenetic clustering and molecular epidemiology;
- 6) To evaluate the prevalence of resistance associated substitutions;
- 7) To determine the sensitivity and specificity of the Xpert® HCV Viral Load assay for HCV RNA detection in samples collected by finger-stick capillary whole-blood.

3. Participant population

Participants will be recruited from tertiary, drug and alcohol and primary health care services in Sydney, Australia.

All patients must be eligible for PBS treatment with elbasvir/grazoprevir as per the prescribing guidelines. In addition the following inclusion and exclusion criteria apply.

Inclusion criteria

- 1) Participants have voluntarily signed the informed consent form.
- 2) Be ≥ 18 years of age on day of signing informed consent form.
- 3) Have chronic HCV genotype 1 or 4 infection (defined as detectable HCV RNA).
- 4) Recent injecting drug use (previous 6 months) or receiving opioid substitution therapy.
- 5) HIV-1 infected subjects enrolled in the study must meet the following criteria:

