6.1 Visits and Procedures

The following assessments must be conducted at study visits as per the schedule of assessments:

Vital signs & physical measurements	Sitting systolic and diastolic blood pressure, heart rate, body weight ^a , height ^a
Fibroscan	Within 12 months prior to screening
Biochemistry	Creatinine, glucose, sodium, chloride, and potassium
Liver Function Tests	ALT, AST, GGT, total bilirubin, albumin, alkaline phosphatase, total protein
Full Blood Count	Haemoglobin, haematocrit, White Blood Cells, platelets, neutrophils
HCV RNA	Must be quantitative at Screening (within 12 weeks prior to Screening) and Week 4
HCV Genotype	Within 12 weeks prior to screening
HBV Serology	Anti-HBc, HBsAg and Anti-HBs testing (within 6 months prior to Screening)
HIV Serology	HIV antibody (within 6 months prior to Screening)
HCG Pregnancy Test	For women of childbearing potential, a negative urine (or serum) HCG test at screening, baseline, weeks 4, 8, week 12 (ETR) and week 14 (home test allowed at week 14)
Questionnaires	Behavioural survey, abbreviated behavioural survey, adherence questionnaire and EQ-5D
Finger-stick point-of-care HCV RNA testing (POC)	At sub-study sites only

^a at screening only

The following assessments and procedures must be performed at each visit as specified below:

Initial screening period (Week -6 to Week 0)

- Informed consent
- Medical history
- Vital signs and physical measurements
- Quantitative HCV RNA and genotype (Local Laboratory)
- LFTs, FBC and biochemistry
- HIV & HBV serology
- Fibroscan
- Pregnancy test (females of child bearing potential only)
- Concomitant medication
- Study questionnaires (Behavioural and EQ-5D)
- Research specimen collection (EDTA plasma & whole blood)
- Finger-stick point-of-care HCV RNA testing (Sub-study sites only)

Baseline visit (Week 0)

- Vital signs and physical measurements
- LFTs, FBC and biochemistry
- Pregnancy test (females of child bearing potential only)
- Serious Adverse Events
- Concomitant medication
- Study questionnaires (Abbreviated Behavioural)
- Research specimen collection (EDTA plasma & whole blood)
- Finger-stick point-of-care HCV RNA testing (Sub-study sites only)

On-Treatment Visits

Week 4 (+/- 7 days)

- Quantitative HCV RNA (Local laboratory)
- Pregnancy test (females of child bearing potential only)
- Serious Adverse Events
- Research specimen collection (EDTA plasma)
- Study questionnaire (Adherence)
- Finger-stick point-of-care HCV RNA testing (Sub-study sites only)

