6.2 Study Questionnaires

All subjects will undertake a number of study questionnaires at screening, baseline, and selected follow-up visits.

The Behavioural Questionnaire

The study staff will assist participants to complete this questionnaire. The behavioural survey will collect information on the following:

- Demographics
- HIV and drug treatment history
- Drug and alcohol usage
- Treatment acceptance and willingness (prior to treatment commencement only)
- Attitudes and behaviours associated with HCV reinfection
- Injecting risk behaviours (including information about injecting sharing partners and equipment sharing)

An abbreviated behavioural questionnaire (follow-up) will be administered at subsequent time points during the study.

Health Outcomes Survey (EQ-5D)

The EQ-5D health questionnaire provides a simple descriptive profile and a single index value for health status. This information can then be translated into a health utility, which can be used for cost-effectiveness analyses.

Adherence Survey

Adherence to elbasvir/grazoprevir will be assessed by a four-weekly structured self-report adherence questionnaire and four-weekly pill count.

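### Injecting during therapy is a listed predictor of SVR12, but it is not scheduled to be asked before Week 12, so participants lost earlier have no value for it

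*Combined protocol and SAP*

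**What the plan says.** Under the primary objective in Section 10, "Factors associated with treatment response (as measured by SVR) will be assessed by univariate and multivariate logistic regression analyses". The candidate factors include "injecting behaviours (recent injecting drug use prior to and during therapy and type of drug injected". Exploratory objective 1 in Section 2 names the same exposure: "To evaluate factors associated with SVR12 (e.g. drug use at baseline and during therapy, adherence".

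Section 6.2 places drug use and injecting risk in the behavioural questionnaire, and says of later visits that "An abbreviated behavioural questionnaire (follow-up) will be administered at subsequent time points during the study". The visit lists in Section 6.1 and the Schedule of Assessments agree on the timing:

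- Screening: full behavioural survey.
- Baseline (Week 0): "Study questionnaires (Abbreviated Behavioural").
- Weeks 4 and 8: "Study questionnaire (Adherence") only.
- Week 12 (end of treatment): "Study questionnaires (Abbreviated Behavioural, Adherence, and EQ-5D").
- Week 24 (SVR12) and later visits: abbreviated behavioural survey again.

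The Week 4 and Week 8 instrument is described as a measure of drug-taking: "Adherence to elbasvir/grazoprevir will be assessed by a four-weekly structured self-report adherence questionnaire and four-weekly pill count". Nothing in that description mentions injecting.

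The documents describe no early-termination visit. They give no rule for a missing SVR12 result and no rule for a missing covariate.

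**The concern.** The Baseline survey is given on the day treatment starts, so it cannot record injecting on treatment. The first scheduled form that can do so is at Week 12. Anyone who leaves for good before then has no value for a predictor that the plan names.

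This missingness is unlikely to be unrelated to the outcome, because a person lost before Week 12 will normally have no SVR12 sample either. If that person is counted as a non-responder, he or she is a failure in the headline proportion and is absent from a standard logistic model of injecting during therapy. The plan expects few non-responders, so losing a handful of them can change the estimate substantially. The gap lies in data collection: values not asked for at the time cannot be restored by a later choice of analysis.

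**Working it through.** **Inputs**

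- N = 150 and SVR12 = 135 of 150 (Section 10, sample size for the primary objective), so 15 non-responders are planned.
- Loss of 20% per year (Section 10, sample size for the secondary objective). It is stated for reinfection follow-up. No rate is given for the 12 treatment weeks, so its use here is an assumption.

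**Step 1. The plan's own figure.** The exact (Clopper-Pearson) 95% interval for 135/150 is 84.04% to 94.29%. The stated 84.0% to 94.3% reproduces, so 15 non-responders of 150 is a sound starting point.

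**Step 2. Losses by visit.** Loss by week t = 1 − 0.8^(t/52).

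- Week 4: 1 − 0.8^(4/52) = 1.7%; 150 × 0.017 = about 2.6 participants.
- Week 12: 1 − 0.8^(12/52) = 5.0%; 150 × 0.0502 = about 7.5 participants.

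**Step 3. Non-responders left in a complete-case model.** Assume that everyone lost before Week 12 is among the 15 non-responders and has no on-treatment injecting value. With k lost, 15 − k of 150 − k remain.

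| Lost before Week 12 | Non-responders left | Records in model |
|---|---|---|
| 0 | 15 | 150 |
| 3 | 12 | 147 |
| 5 | 10 | 145 |
| 7 | 8 | 143 |
| 8 | 7 | 142 |
| 10 | 5 | 140 |

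At the 20% annual rate (7 or 8 lost), about half of the non-responders leave the model.

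**Step 4. Direction of bias.** Take an assumed example with two groups of 75, with 10 failures in those injecting on treatment and 5 in the others. The full-data odds ratio for failure is (10/65)/(5/70) = 2.15. Now remove seven failures as early losses:

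| Lost: injecting / not injecting | Complete-case odds ratio |
|---|---|
| 4 / 3 | (6/65)/(2/70) = 3.23 |
| 5 / 2 | (5/65)/(3/70) = 1.79 |
| 6 / 1 | (4/65)/(4/70) = 1.08 |
| 7 / 0 | (3/65)/(5/70) = 0.65 |

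The same number of losses can exaggerate, shrink or reverse the association, depending on who is lost. With the missing values unrecorded, the data could not show which of these had happened.

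**The case against.** Several arguments on the other side stand and limit the point.

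- A reader might infer that early drop-outs are non-responders under the plan and are dropped from the model. Neither is written. The endpoint is a proportion of participants, which points towards counting them, but no missing-equals-failure rule appears. If participants without an SVR12 result were excluded instead, they would leave the model for lack of an outcome, whatever had been asked at Week 4. Complete-case analysis is the software default, not a stated choice.
- A reader might infer that the model would wrongly show no effect of injecting. One can build such a case: drop-out of 8% against 2%, with 8% failure in both groups of completers, gives a full-data odds ratio of 1.66 and a complete-case one of 1.0. The second figure follows from the equal failure rates put in. Step 4 shows that other patterns give other answers.
- A reader might add the 7.5 losses to 10% failure among the other 142.5 and arrive at about 22 non-responders (7.5 + 14.25). That treats 90% as a rate among completers. Section 10 calls it the overall SVR, so the plan implies 15.
- The exposure is missing because a visit is missed, not because treatment failed. Someone who stops the drug but attends Week 12 is surveyed. Someone who skips Week 12 and returns at Week 24 is surveyed then, although the recall period of that form is not in the documents.
- The adherence form itself is not in the documents, so an injecting item on it cannot be fully excluded.
- Injecting before therapy is collected at Screening and Baseline and remains usable as a predictor.

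These points bear on the size and direction of the problem. They do not supply a scheduled on-treatment injecting value for a participant who is lost before Week 12.

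**Conclusion.** The point holds as a gap in data collection for one named predictor analysis. A participant lost for good before Week 12 has no scheduled value for injecting during therapy. If such participants count as non-responders and the model is complete-case, 3 to 10 losses leave 12 down to 5 of the 15 planned non-responders in it. The central illustration of about 7.5 losses borrows a rate stated for another phase. The resulting bias has no known direction.

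The primary SVR12 proportion is not threatened, and neither is the analysis of baseline injecting. The documents do not support saying that the plan would hide an effect of injecting, or that it classifies drop-outs as failures. The improvement is worth making because it is cheap and cannot be made after the visits have passed.

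**What to change.** 1. Add the injecting items of the abbreviated behavioural survey to the existing Week 4 and Week 8 questionnaires. On the same assumed loss rate, the number with no on-treatment value falls from about 7.5 to about 2.6 of 150, namely those lost before Week 4.
2. Define injecting during therapy as any injecting reported at any on-treatment visit. Using only the latest report would classify completers from Week 12 and early leavers from Week 4 or 8. If the items cover the time since the last visit, a completer who injected only early would then count as a non-injector, and the exposure window would depend on drop-out.
3. Completers will still have more chances to report injecting than early leavers. Add a sensitivity analysis that uses the Week 4 report alone, so that the window is the same for both.
4. State that participants without an SVR12 result are handled in the predictor model as they are in the primary proportion.

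The cost is one or two extra questions at two visits that already include a questionnaire, a minor form amendment, and a few sentences in Section 10. The added reports would also serve exploratory objective 4, on injecting risk behaviours during treatment, which at present has Week 12 as its only scheduled survey after treatment starts and before follow-up.
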